### 5 Treatment

---

For this study, intravenous iron isomaltoside (Monofer®) and matching placebo are defined as investigational medicinal products.

#### 5.1 Drug identity, supply and storage

---

*Medication and comparator*

Active drug: Intravenous iron isomaltoside dissolved in 100 ml NaCl 0.9 %.  
Placebo: Intravenous sodium chloride 0.9%; 100 ml.

*Supply, packaging, labelling, handling, storage and accountability*

The manufacturer supplies study medication to the investigators on site. It is labelled with information according to local regulation. The study medication will be stored in a locked refrigerator (2-8°C), protected from unintended use. All study medications supplied for this trial will be retained in a safe place at all times of the study. Only personnel authorised by the principal investigator should dispense the study medication, and the accountability is the responsibility of investigator. An up to date study medication inventory (dispensing records) will be maintained at all times.

## 5.2 Dosage and administration

---

After the participant has provided informed consent, he or she will be randomised to receive a single intravenous administration of iron isomaltoside (Monofer®) or matching placebo. The active drug, iron isomaltoside, will be administered as a single, intravenous infusion of 20 mg/kg body weight (rounded off to the nearest 100 mg) dissolved in 100 ml NaCl as recommended by the drug manufacturer ("on-label" treatment). Patients allocated to placebo will receive an intravenous infusion of 100 ml NaCl 0.9% administered in the same manner. Because iron isomaltoside is a dark-brown solution that is easily distinguishable from the saline placebo, study personnel responsible for the preparation and administration of the study drug will be aware of the group assignments and will therefore not be involved in any study assessments. To ensure that patients are unaware of treatment allocation, we will cover the injection site, syringes and intravenous lines with sheets to shield the injection site from the patient's view

The active drug dilution/placebo will be prepared and administered, according to the randomisation code, by nurses who do not participate in the trial. The investigational medicinal products will only be administered when staff trained to evaluate and manage anaphylactic reactions is immediately available, in an environment where full resuscitation facilities can be assured. The patients will be observed for adverse effects for at least two hours following the injections.

## 5.3 Duration of therapy

---

The investigational medicinal products (iron isomaltoside or placebo) will be administered as a single intravenous infusion over 30 minutes only (1,67 ml/min). No other study-specific intervention will be provided. For intravenous iron, a single dose of 20 mg/kg is expected to provide adequate iron supplement in patients with haemoglobin above 100 mg/l.

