### **5.7 Drug labelling**

---

The investigational product will have a label permanently affixed to the outside and will be labelled according with ICH/GCP and national regulations, stating that the material is for clinical trial / investigational use only and should be kept out of reach of children.

The bag with the dissolved solution will have an affixed label stating (in Norwegian)

This bag contains ... mg iron isomaltoside or placebo (Study drug number ...) dissolved in 100 ml NaCl 0.9 % for the IronIC trial. The drug is meant for intravenous administration over 30 minutes (1.67 ml/min). The content of this bag was prepared by ... .

Labels will also include blank lines (in Norwegian) for:

Patient's initials  
Patient's study number  
Date dispensed  
Name of prescribing doctor

"Denne posen inneholder ... mg jernisomaltosid eller placebo (studiemedikamentnummer ...) i 100 ml 0,9 % NaCl til bruk i IronIC-studien. Posen skal gis intravenøst i 30 minutter (1,67 ml/min). Denne posen ble tilberedt av \_\_\_\_\_.

Pasientens initialer: \_\_\_\_\_  
Studienummer: \_\_\_\_\_  
Dato: \_\_\_\_\_  
Forskrevet av dr: \_\_\_\_\_  
»

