### 8.1.2 Adverse events of special interest (AESI)

In general, AESIs are AEs that occur in categories of special interest with regard to determining the benefit/risk profile and overall safety of a drug. Two kinds of AEs are of particular concern regarding intravenous iron infusions:

- Hypersensitivity/anaphylactic reactions: Infusion with Monofer® can result in acute hypersensitivity reactions characterised by hypotension and signs of anaphylaxis. These reactions may occur even in patients who have had previous, uneventful iron infusions, and are more common in patients with allergic diatheses or autoimmune diseases.
- Skin discolouration: Paravenous leakage may cause skin irritation and long-lasting discolouration.

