5.4 Randomisation and Blinding

Balanced, permuted block randomisation (in a 1:1: ratio for the two study arms) using random block sizes was computed by the Research Support Unit at Oslo University Hospital. A complete, sealed randomisation list containing details of all patient numbers and study group is stored as essential documentation within the Trial Master File in a locked office. Treatment allocation is performed by random draw of sealed, opaque envelopes containing cards marked "iron isomaltoside 20 mg/kg" or "placebo". A nurse who does not participate in the trial or has competing interest regarding study outcomes prepared the envelopes and has exclusive access to the list linking study drug numbers, and batch numbers and expiry dates. The administration of the study drug is performed by nurses who are not part of the study team. The study participants (patients) and all study personnel, including investigators, personnel assessing outcomes, study nurses, data analysts and treating physicians and nurses, are blinded to allocation to study drug.

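### The infusion volume (100 ml), duration (30 minutes) and rate (1.67 ml/min) cannot all be right: they conflict by a factor of two, in the protocol text and on the bag label in both languages.

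*Protocol*

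**What the plan says.** The volume is 100 ml wherever one is given. Protocol 5.1 has "Active drug: Intravenous iron isomaltoside dissolved in 100 ml NaCl 0.9" %, with 100 ml of saline as placebo. Section 5.2 repeats this for the active drug and adds: "Patients allocated to placebo will receive an intravenous infusion of 100 ml NaCl 0.9% administered in the same manner".

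Duration and rate appear together three times:

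- Protocol 5.3: "administered as a single intravenous infusion over 30 minutes only (1,67 ml/min").
- Protocol 5.7, English label text: "The drug is meant for intravenous administration over 30 minutes (1.67 ml/min").
- Protocol 5.7, Norwegian label text: "Posen skal gis intravenøst i 30 minutter (1,67 ml/min").

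Both label texts also state the 100 ml volume, so the label carries all three figures side by side.

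The dose is clear. Section 5.2 sets 20 mg/kg, section 5.3 says "a single dose of 20 mg/kg is expected to provide adequate iron supplement", and the allocation cards carry the same dose (protocol 10.2.2; in SAP 5.4, "iron isomaltoside 20 mg/kg"). The SAP gives no infusion volume, duration or rate.

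**The concern.** Any two of volume, duration and rate determine the third, and here the third does not follow. A nurse who sets a pump to the stated rate and one who runs the bag in over the stated time would both be following the label, yet would deliver iron at speeds that differ twofold.

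This is the administration instruction for the only dose in the trial. Section 5.2 assigns preparation and administration to nurses who do not take part in the trial, so the label is likely to be a main instruction at the bedside. The speed of infusion should be unambiguous because section 8.1.2 lists hypersensitivity as an adverse event of special interest: the product "can result in acute hypersensitivity reactions characterised by hypotension and signs of anaphylaxis". If a reaction occurred, the protocol as written would not show what rate had been prescribed, or whether the patient had been treated according to it.

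**Working it through.** **Inputs.** Volume V = 100 ml (protocol 5.1, 5.2 and both label texts in 5.7). Duration T = 30 min and rate R = 1.67 ml/min (5.3 and both label texts). Dose D = 20 mg/kg (5.2, 5.3).

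**Can the stated rate be reproduced?** Rate = V/T = 100/30 = 3.33 ml/min, not 1.67. The ratio is 3.33/1.67 = 2.00.

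**Holding two figures and solving for the third**

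| Held fixed | Formula | Result | Stated |
|---|---|---|---|
| 100 ml, 30 min | V/T = 100/30 | 3.33 ml/min | 1.67 ml/min |
| 100 ml, 1.67 ml/min | V/R = 100/1.67 | 59.9 min | 30 min |
| 30 min, 1.67 ml/min | R × T = 1.67 × 30 | 50.1 ml | 100 ml |

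**Where 1.67 could come from.** 100/60 = 1.67, so the rate fits a 60-minute infusion of the stated volume. 50/30 = 1.67 also fits, but no section mentions 50 ml.

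**Does drug concentrate explain it?** The documents do not say whether the concentrate adds to the 100 ml. If it added 5 to 25 ml (an assumption), the rate needed for 30 minutes would be 105/30 = 3.50 to 125/30 = 4.17 ml/min, which is further from 1.67.

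**Rate of iron delivery**

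- Whole bag in 30 min: 20/30 = 0.67 mg/kg/min.
- Whole bag at 1.67 ml/min: 20/59.9 = 0.33 mg/kg/min.

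The documents give no body weights. For assumed weights of 60, 80 and 100 kg:

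| Weight | Dose | In 30 min | In 59.9 min |
|---|---|---|---|
| 60 kg | 1200 mg | 40.0 mg/min | 20.0 mg/min |
| 80 kg | 1600 mg | 53.3 mg/min | 26.7 mg/min |
| 100 kg | 2000 mg | 66.7 mg/min | 33.4 mg/min |

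**If rate and time were both followed literally** and the rest of the bag discarded, the dose given would be 20 × 50.1/100 = 10.0 mg/kg.

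**The case against.** The strongest reply is that this is a misprinted derived figure of little consequence. In all three places the duration is the instruction and the rate only a bracketed gloss on it; section 5.3 stresses that the 30 minutes is a limit; and no section mentions 60 minutes. The Norwegian label says that the bag is to be given, which argues against anyone stopping halfway. Nothing in the documents shows that either speed is unsafe, since no maximum rate is stated. Both arms share the instruction, and no endpoint, sample-size or analysis element depends on infusion rate. The safeguards are substantial: staff trained to manage anaphylaxis and resuscitation facilities (5.2), vital signs recorded during the infusion (7.2), and at least two hours' observation (5.2, 5.4).

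Most of this stands. Thirty minutes is the likelier intention, a half dose is possible but not demonstrated, and the documents do not show which rate is safer. It does not remove the contradiction, which is printed on the label, and a pump is set by rate. That 1.67 is exactly 100/60 also means that a 60-minute infusion cannot be excluded from the text.

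A narrower objection is that 3.33 ml/min empties the bag in 30 minutes only if its final volume is exactly 100 ml. That is correct, but the documents give no concentrate volume, and any such volume would widen the mismatch.

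**Conclusion.** The concern holds. The conflict is exactly twofold once rounding is allowed for. It needs only the protocol's own figures and does not depend on the assumed weights. The text does not settle whether the rate or the duration is wrong.

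The likely consequence is that the full 20 mg/kg is given at a rate or over a time that differs twofold from one of the stated figures, possibly differently from patient to patient. Administration of about 10 mg/kg would require a nurse to follow rate and time literally and leave half the bag. No bias in the primary comparison follows, because placebo is given in the same way. The error should be fixed because it sits in the operative instruction for the trial's only dose and is cheap to correct.

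**What to change.** Keep the 100 ml volume. Then either correct the rate to 3.33 ml/min, if 30 minutes is intended, or correct the duration to 60 minutes, if 1.67 ml/min is intended. Make the same change in protocol 5.3 and in the English and Norwegian label texts in 5.7, and state in each that the whole bag is to be given. The sponsor should take the choice from the intended administration instructions, since the documents do not decide it. If the concentrate adds to the 100 ml, the final bag volume should be stated and the rate worked out from it.

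The cost is one corrected figure in three places, one added sentence and a reprinted label, handled through the amendment procedure in protocol 11.3. No extra patients, visits or staff are needed.

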## 5.4 Monitoring during drug administration

---

The study drug will be administered in a hospital setting, with frequent attendance by experienced nurses. Vital signs are observed and documented prior to study drug infusion. The patients will be hospitalised for at least two hours after the study drug infusion, and thereafter for as long as deemed necessary by the responsible physician.

## 5.5 Concomitant medication

---

All concomitant medication (incl. vitamins, herbal preparation and other "over-the-counter" drugs) used by the patient will be recorded in the patient's file and CRF. Study participation does not preclude administration of drugs that are provided on clinical indication. On the contrary, study participants will receive standard-of-care treatment as recommended in prevailing guidelines. Concurrent treatment with steroids other than low doses of corticosteroids (equivalent to 10 mg prednisone or less) at the time of randomisation is an exclusion criterion. New immunosuppressants should not be introduced within the first month after randomisation unless necessary as deemed by the treating physician.

### **5.5.1 Prohibited treatments during study period**

---

The following treatments are not permitted during the study:

- parenteral iron supplement (other than the initial study drug infusion)
- oral iron substitution

### **5.6 Drug accountability**

---

The responsible site personnel will confirm receipt of study drug and will use the study drug only within the framework of this clinical study and in accordance with this protocol. The manufacturer (Pharmacosmos®) provides the active study drug. The study drug or matching placebo will be administered by trained hospital personnel. The manufacturer supplies study medication to the investigators on site. It will be labelled with information according to local regulation. The study medication will be stored in a locked refrigerator (2-8°C), protected from unintended use. All study medications supplied for this study must be retained in a safe place at all times of the study. Only personnel authorised by the principal investigator should dispense the study medication, and the accountability is the responsibility of investigator. A study medication inventory (dispensing records) for all medication dispensed must be maintained at all times. A unique, three-digit number will be assigned to each study drug dose (iron isomaltoside or placebo) by an independent nurse. The study drug number and drug dose (sham dose if placebo) will be available in the patient file. A list linking study drug numbers and batch-numbers and expiry dates will be kept in a sealed envelope in a locked closet, but can be opened if unblinding is necessary (see paragraph 10.2.3). The study drug inventory must contain information on Monofer® vial batch numbers and expiration dates. A study nurse will be responsible for drug storage, including keeping a temperature log, and the study drug inventory.

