## 6.2 By visit

Study participants will be recruited from the pool of heart transplant recipients who attend regular follow-up at Oslo University Hospital, Rikshospitalet. A dedicated study nurse not responsible for the routine treatment of the patients, will ask eligible patients to participate when clinical assessment, ferritin/transferrin and safety blood samples (routine blood samples in heart transplant recipients) have been performed and analysed.

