#### **10.2.2 Allocation- procedure to randomise a patient**

---

We will use a computerised randomisation procedure for treatment allocation. Patient randomisation will be performed by random draw of sealed, opaque envelopes containing cards with the words “iron, 20 mg/kg” or “placebo (study drug no. ...)” once eligibility has been confirmed and the informed consent form has been signed. The study drug numbers will be assigned to each drug vial (or placebo card) by a nurse who does not participate in the trial or have competing interest regarding study outcome. This nurse will have exclusive access to the list linking study drug numbers, and batch numbers and expiry dates. According to the randomisation list, unique cards marked “iron, 20 mg/kg” or “placebo (study drug no. ...)” will be placed in sealed, opaque envelopes by a nurse not participating in the trial. A copy of the randomisation list will be stored in a sealed, opaque envelope in a locked cupboard along with the study drugs, a mechanism employed to minimise the possibility that those enrolling and assigning patients will obtain access to the list.

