#### **10.2.3 Blinding and emergency un-blinding**

---

The study participants (patients) and all study personnel, including investigators, personnel assessing outcomes, study nurses, data analysts and treating physicians and nurses, will be blinded to allocation to study drug. Only the non-investigating nurse(s) preparing and administering the study drug at randomisation will be aware of treatment allocation.

Un-blinding will be performed in the event of AEs where knowledge of the type of drug might be of importance to the personnel treating the patients, and in the event of SUSARS. Un-blinding will be performed by non-investigating personnel without competing interest, and the result will immediately be reported to the primary investigator, who will then take the required action(s). Unless unavoidable, other investigators and personnel assessing outcomes should not be made aware of treatment allocation.

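### Storage and inventory of Monofer are given to a study nurse, a role declared blinded, although vial use would let that nurse infer individual allocations

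*Protocol*

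**What the plan says.** Protocol Section 5.6 allocates the task: "A study nurse will be responsible for drug storage, including keeping a temperature log, and the study drug inventory". The same section makes that inventory a running dispensing record, which has to show batch and expiry details of the Monofer vials. Section 5.1 also requires it to be kept current.

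Protocol Section 10.2.3 states that "all study personnel, including investigators, personnel assessing outcomes, study nurses, data analysts and treating physicians and nurses, will be blinded to allocation". It then gives one exception: "Only the non-investigating nurse(s) preparing and administering the study drug at randomisation will be aware of treatment allocation". SAP Section 5.4 repeats the blinding statement ("study nurses, data analysts and treating physicians and nurses, are blinded to allocation to study drug") and has no exception for whoever keeps the stock.

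Three further places bear on the point:

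- Protocol Section 5.2 bars from study assessments the staff who prepare and give the infusion, because the iron solution is visibly different from saline. It does not mention staff who store or count the drug.
- Protocol Section 6.2 describes recruitment: "A dedicated study nurse not responsible for the routine treatment of the patients, will ask eligible patients to participate".
- Protocol Section 10.2.2 says: "A copy of the randomisation list will be stored in a sealed, opaque envelope in a locked cupboard along with the study drugs".

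**The concern.** The plan takes care to hide the product. Lines and injection site are covered, a sham dose is filed for placebo patients, and the list that links study drug numbers to batches is sealed. The stock record needs the same care, because in this trial the two arms draw on different stock. If the keeper of that record belongs to the study team, the team is not blind in the way that Protocol Section 10.2.3 and SAP Section 5.4 state.

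What would be at stake depends on what else that nurse does. Peak oxygen consumption is measured to volitional fatigue, and a test can count as adequate on the Borg score (Protocol Section 7.1.1). SAP Section 7.2.1 leaves inadequate tests out of the primary analysis and relies on adequacy being settled before the code is opened. That safeguard works only if those who settle it do not already know the arms. If the nurse also recruited, knowledge of past allocations could reach the point of enrolment.

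**Working it through.** The plan gives no figure on this point, so the check is a comparison of the relevant sections.

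**1. Who holds the stock?** Protocol 5.6: a study nurse, for storage, temperature log and inventory.

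**2. Is that role blinded?** Protocol 10.2.3 and SAP 5.4: yes, study nurses are named.

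**3. Is there an exception that covers the task?** Protocol 10.2.3 exempts non-investigating nurses who prepare and administer the drug. Storage and inventory are neither of these, and a study nurse is not described as non-investigating. No exception applies.

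**4. Does the record separate the arms?**
- Protocol 5.1: placebo is 100 ml of saline, so a placebo infusion uses 0 Monofer vials.
- Protocol 5.2: the iron dose is set by body weight and is above zero at any weight, so an iron infusion uses at least 1 vial.
- Protocol 10.2.2 makes the same distinction, since drug numbers go to a vial in one arm and to a placebo card in the other.

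Vial movement is therefore at least 1 for iron and 0 for placebo. This step is an inference, but it needs no assumption about weight or vial size.

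**5. Can stock be matched to patients?** The target is 100 patients (Protocol 4.2) over a planned 12 months of recruitment (Protocol Section 3), so 100 / 52 = about 1.9 per week on average. At that pace a record kept current could often be set against single infusions. Two patients treated between stock checks would be harder to tell apart. The documents do not describe the layout of the record, so the supportable wording is that the nurse could infer allocations.

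**6. Is the holder kept away from recruitment and assessment?** The bar in Protocol 5.2 covers preparing and administering staff only. Protocol 6.2 refers to a dedicated study nurse who approaches patients, and Protocol 5.6 to a study nurse who keeps the stock. No section says that they are the same person, and none says that they are different.

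**7. Where is the list copy?** Protocol 10.2.2 puts it in a sealed, opaque envelope in a locked cupboard with the drugs, whereas Protocol 5.1 and 5.6 put the drugs in a locked refrigerator. The two descriptions of the store do not match.

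**The case against.** The strongest reply is that this is a gap in wording and not demonstrated unblinding. The documents give the stock nurse no part in the treadmill test or any other assessment. Section 10.2.3 names outcome assessors separately from study nurses. Patients, who complete the quality-of-life forms, are shielded by covered lines. Doses carry numbers in both arms, and the linking list is sealed. All of this stands, and it limits the point to what the nurse could infer and to the missing separation of roles. It does not remove the conflict between Protocol 5.6 and 10.2.3.

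A reader might also infer more than the text supports:

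- *That Protocol 10.2.2 forbids this nurse to see batch numbers.* The sentence is "This nurse will have exclusive access to the list linking study drug numbers, and batch numbers and expiry dates". It restricts the list that makes the link, not batch numbers as such, so a stock record that shows batches does not contradict it.
- *That the nurse has the randomisation list to hand.* The copy is sealed and locked away, and whether it shares the drug store is unclear. Being near a sealed envelope is not knowing what is in it.
- *That the recruiting nurse is the stock nurse and can predict the next allocation.* Their identity is not stated. Random block sizes (Protocol 10.2.1, SAP 5.4) also limit prediction even for someone who knows the past sequence.
- *That every patient's arm would be known with certainty.* That would need stock to be matched to each patient as treatment happens, which the documents do not describe.

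**Conclusion.** The concern holds in limited form. The contradiction is certain on the text: a role declared blinded in both documents is given a task outside the only exception in Protocol 10.2.3. That the task could reveal allocations follows from the saline placebo and a current record of Monofer vials. It rests on two assumptions: that the inventory is kept as up to date as the protocol requires, and that nothing in its layout or in physical access to the store hides use per patient.

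The exposure is one role, with possible knowledge of allocation across the patients treated while that person holds it. No effect on the primary result can be calculated, and none is shown. Whether recruitment or outcome assessment is touched depends on who holds the role in practice, which the documents leave open. The change is worth making because the route can be closed at little cost. The place where the list copy is kept is a secondary matter.

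**What to change.** 1. In Protocol 5.6, assign storage, temperature log, inventory and vial reconciliation to the non-participating, unblinded nurses already in the design. Protocol 5.2 has such nurses preparing and giving the infusions, and Protocol 10.2.2 has one who assigns drug numbers and holds the linking list. The documents do not say that these are the same person, so the text should state which of them takes the task.
2. State that whoever holds the task takes no part in recruitment or in any study assessment, which extends the bar in Protocol 5.2.
3. Keep blinded study nurses out of the drug store and the inventory until the code is opened.
4. Align Protocol 5.6 and 10.2.3 and SAP 5.4, so that the exception to blinding covers the storage and inventory role.
5. As a secondary precaution, keep the sealed copy of the randomisation list away from the drug store. A complete list is already held with the Trial Master File in a locked office (Protocol 10.2.1). Reconcile the refrigerator wording in Protocol 5.1 and 5.6 with the cupboard wording in 10.2.2.

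The cost is a small added duty for nurses outside the trial team, an entry in the delegation list, and edits to a few sentences in the two documents. Sample size, assessments and analysis do not change.
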